Hypothesis 3a. Mixed effects modeling will be used to test the hypothesis that participants randomized to the intervention groups (ESBR-i and ESBR-v) will show longer community tenure compared to UC over time. In mixed effects analyses, days of community tenure will be modeled as the key dependent variable predicted by the group membership (ESBR-i and ESBR-v vs. UC). The model will be adjusted for effects of care recipient gender, income, and disease stage (Global Deterioration Scale score). The effects of other potential covariates including caregiver and patient age, caregiver gender, dementia subtype, and caregiver burden and depression will also be explored.

Hypothesis 3b. Cox proportional hazards regression modelling [70] will be used to test the hypothesis that Veterans with family caregivers randomized to the intervention groups (ESBR-i and ESBR-v) will transition to LTC at a slower rate compared to UC. In proportional hazards regression analyses, time to permanent LTC placement (total time from caregiver randomization to permanent LTC placement of the care receiver) will be modelled as the key dependent variable predicted by the group membership (ESBR-i and ESBR-v vs. UC). The model will be adjusted for effects of care recipient gender, income, and disease stage (Global Deterioration Scale score). The effects of other potential covariates including caregiver and patient age, caregiver gender, dementia subtype, and caregiver burden and depression will also be explored.

Hypothesis 3c. Cox proportional hazards regression modelling [70] will be used to test the hypothesis that Veterans with family caregivers randomized to the intervention groups (ESBR-i and ESBR-v) will survive longer compared to UC. In proportional hazards regression analyses, time to death (total time from caregiver randomization to death of the care receiver) will be modelled as the key dependent variable predicted by the group membership (ESBR-i and ESBR-v vs. UC). The model will be adjusted for effects of care recipient gender, income, and disease stage (Global Deterioration Scale score). The effects of other potential covariates including caregiver and patient age, caregiver gender, dementia subtype, and caregiver burden and depression will also be explored.

Exploratory Aims:

Hypothesis 4. Mixed effects modeling will be used to examine whether participants who receive the intervention via video telehealth (ESBR-v) will show similar levels of caregiver burden compared to those that receive the intervention in-person (ESBR-i) over time. For this exploratory aim, we will focus on monitoring the clinical significance (effect size). We expect the effect size will be quite small (Cohen's *d* of 0.2 or less). In mixed effects analyses, the change in caregiver burden (ZBI total score) will be modeled as the key dependent variable predicted by the group membership (ESBR-i vs. ESBR-v).

Mixed effects modeling will be used to examine whether participants who receive the intervention via video telehealth (ESBR-v) will show similar levels of caregiver depression compared to those that receive the intervention in-person (ESBR-i) over time. For this exploratory aim, we will focus on monitoring the clinical significance (effect size). We expect the effect size will be quite small (Cohen's *d* of 0.2 or less). In mixed effects analyses, the change in caregiver depression (CES-D total score) will be modeled as the key dependent variable predicted by the group membership (ESBR-i vs. ESBR-v).

Mixed effects modeling will be used to test the hypothesis that participants who receive the intervention via video telehealth (ESBR-v) will have similar community tenure compared to those that receive the intervention in-person (ESBR-i) over time. For this exploratory aim, we will focus on monitoring the clinical significance (effect size). We expect the effect size will be quite small (Cohen's *d* of 0.2 or less). In mixed effects analyses, community tenure (time spent living in the community) will be modeled as the key dependent variable predicted by the group membership (ESBR-i vs. ESBR-v).

Cox proportional hazard modeling will be used to test the hypothesis that Veterans with caregivers who receive the intervention via video telehealth (ESBR-v) will show similar rates of LTC placement and survival compared to those that receive the intervention in-person (ESBR-i) over time. In Cox proportional hazard models, LTC placement or survival will be modeled as the key dependent variable predicted by the group membership (ESBR-i vs. ESBR-v).

Hypothesis 5. Clinico-demographic characteristics (e.g., caregiver age, dementia type/severity, socioeconomic status) will be evaluated as moderators of the effects of the ESBR intervention (i.e., Aims 1, 2, and 3). For this investigation, the MacArthur framework for moderator analysis [71] will be embedded in mixed effects and Cox proportional hazards models. The moderator effect will be tested in line with the eligibility and analytical criteria described in Kraemer et al. [71].]]

2.A.3.e.8b. Power Estimation

We estimated power based on the proposed mixed effects analyses considering the repeatedly measured outcomes. Based on these analyses, we converted the growth model parameter estimated to group difference in primary outcome at 12 month. Considering potentially nonlinear development of our outcomes, we allowed for nonlinear trend over time (specifically, we used a piecewise growth model). In our power estimation for primary hypothesis 1, over the 4 assessments, we assumed the attrition rate of 10% (6 month), 15% (12 month), and 20% (24 month). We assumed the reliability of the Zarit Burden Interview to be 0.7 based on prior studies demonstrating a range of intra-class correlation coefficients that vary based on time intervals between tests [59-61]. Prior studies of caregiver interventions, like many psychosocial interventions, have reported small to medium effect sizes. One such study specifically aimed to improve outcomes of caregivers of Veterans with all-cause dementia of the Alzheimer's type [23] and demonstrated effect sizes (Cohen's *d*) on caregiver burden and depression ranging from 0.26-0.33. Based on this study, we expect an effect size of $d=0.3$ on our primary outcome of caregiver burden, as measured by the Zarit Burden Interview [72], and designed our study to be powered accordingly assuming that mixed effects modeling will be used as the analysis method. Our primary hypothesis (Hypothesis 1) is that those in the intervention group ($n=50$ ESBR-i and $n=50$ ESBR-v) will show steeper decline in burden compared to the usual care ($n=50$ control) group. Under this scenario, the estimated power to detect the difference between the intervention (ESBR-i + ESBR-v) and the control group in terms of care burden is 0.83 ($d=0.3$, $\alpha=0.05$, two-tailed) at the 12-month follow-up. For the secondary analysis, we will monitor both clinical (effect size) and statistical (p -value) significance, with more emphasis on clinical significance, which will inform future trials.

2.A.3.e.9. Implementation Plan

The table below presents a general outline of the activities planned during the award period to ensure timely completion of the research plan, publication/presentation of results, preparation of future studies aiming to enhance Veteran- and family-centered care (i.e., VA Merit Award), and development of a dissemination plan for a successful intervention.

CDA-2 TIMELINE										
	Year 1		Year 2		Year 3		Year 4		Year 5	
Project Component										
Study preparation	X									
Recruit/screen participants	X	X	X							
Data collection		X	X	X	X	X	X	X	X	
Data analysis			X	X	X	X	X	X	X	
Manuscript preparation				X	X	X	X	X	X	X
Presentation of findings				X	X	X	X	X	X	X
Merit award preparation							X	X	X	X

2.A.3.e.10. Dissemination Plan

If this form of ESBR were shown to be useful in improving outcomes in dementia caregivers or Veterans with all-cause dementia, it could easily be assimilated into our national roll-out program at the VISN 21 MIRECC. The Evidence-Based Therapy (EBT) roll-out started with cognitive-behavioral therapy for depression (CBT-D), then progressed to include CBT for insomnia (CBT-I). The program has now trained over 1,500 VA therapists nation-wide. The program staff consists of a national coordinator based in VACO, a coordinator based at VAPAHCS, and several staff at VAPAHCS who deal with screening mental health staff applicants for their eligibility to participate, scheduling courses, making sure all course materials are distributed, attending to the administrative arrangements for training sessions and payment of consultants. In general, a 3-day course is given for about 40 VA therapists from 3-4 VISNs in a convenient location. There they meet their “consultants” who will follow the trainee’s treatment of two training patients over a 3-4 month period. Taped recordings of trainees’ therapy sessions are used by consultants to follow trainee proficiency and patient outcomes obtained.

If the results of the proposed study are positive, group trainings (similar to those for CBT-D and CBT-I) of clinicians could be initiated using the same administrative mechanisms, 3-day course model, expert consultant model, and tape-recorded verifications. Thus, if ESBR were to prove useful, we could add this as another intervention disseminated through the EBT program.

2.A.3.e.11. Study Limitations and Potential ProblemsSample Size

One limitation of the current proposal is the relatively small sample size (ESBR-i: n = 50; ESBR-v: n = 50; UC: n = 50). Nonetheless, our power analyses (see Section 2.A.3.e.8b.) indicate we will have ample power to detect intervention effects on the primary outcome of caregiver burden at 12-month follow-up.

Control Condition

Another limitation of the current proposal is our control condition. While we would like to have offered the ESBR intervention (or something more substantial than printed educational materials and resource contact information) to all participants at some time during the study period, this would have made our aims of comparing ESBR to standard VA dementia care unobtainable.

Recruitment

One potential problem may be difficulty recruiting sufficient numbers of family caregivers of Veterans with all-cause dementia. As discussed in Section 2.A.3.c., a strength of our recruitment capability is the integrated network of recruitment support available in clinics and centers staffed/administrated by Key Personnel. Given our past history of participant recruitment/retention at MIRECC and participant response to a pilot of the intervention (see Section 2.A.2.c.), we expect ample ability to meet recruitment/retention goals from these resources. However, we will supplement our veteran sample with non-Veterans, recruited from the San Francisco Bay Area, including our academic affiliate, Stanford University School of Medicine, if necessary.

":00

F
u
n
d
i
n
g
O
p
p
o
r
t
u
n
i
t
y
N
u
m
b
e
r
:
R
X
-
1
3
-
0
0
9
R
e
c
e
i
v
e
d
D
a
t
e
:
2
0
1
3
-
0
6
-
0
!
1
:
1
:
0
6
-
0

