Telephone Cognitive Screen (T-CogS)T. The T-CogS was originally referred to as the Telephone Mini-Mental State Examination (TMMSE) [42]. The T-CogS is a 26-item, brief mental status examination that was designed to be administered over the telephone, based on the Mini-Mental Status Examination (MMSE) [43]. Scores range from 0-26. Scores on the T-CogS are strongly correlated with MMSE scores ($r = 0.88$, $p < 0.001$) [44]. An exclusion cutoff score of < 20 on the T-CogS was chosen to match a MMSE cutoff of < 23 . A telephone cognitive screen was specifically chosen to reduce travel burden for caregivers. **[[Caregivers with a T-CogS score < 20 during screening, or any point during the study, will be offered referrals to the Stanford/VA Alzheimer's Research Center, with full support from Drs. [name] (Director) and [name] (Co-Director and CDA-2 Primary Mentor). The Center provides a comprehensive diagnostic evaluation, including cognitive assessment, by a multidisciplinary clinical research team at no cost to the patient.]]**

The results of all screening assessments will be review with Drs. [name] and [name] in consultation with Drs. [name] and [name]. After consensus determination of study eligibility, the Study Coordinator will contact the participant to schedule a Baseline assessment (if eligible), or provide appropriate referral (e.g., VA Caregiver Support Program) and explanation (if not deemed eligible). Both “screen failures” and eligible participants who drop out prior to receiving any intervention will be replaced.

2.A.3.e. Procedures Involving Eligible Participants

2.A.3.e.1. Enrollment, Randomization, and Baseline Measures

Enrollment and Randomization

Once participants pass screening, they will be invited by the Study Coordinator to participate in the study, if willing and able to provide informed consent *F*. At this point, the Data Manager will **[[randomize the participant to one of the three arms: ESBR-i, ESBR-v, or UC.]]** For randomization, a modification of the Efron procedure [45] developed by [name] [46] will be implemented to assure the three groups are comparable at baseline in terms of dementia subtype. Participants who drop out after receiving any intervention will not be replaced, but their data will be used in mixed-effects analyses (as described in Section 2.A.3.e.8a.).

Baseline Assessment

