Trained study staff, blind to the participants’ ESBR/UC assignment, will administer a baseline assessment including clinicodemographic updates and measures of caregiver burden, depression, self-efficacy, and health-related quality of life, in addition to care recipient functional status (see section 2.A.3.e.6. for a detailed description of these measures). These assessments will mainly occur over the telephone. Our motivation for telephone assessment is to reduce study participation burden for the participants. Packets with assessment aids will be sent to the caregiver in the mail prior to each assessment. **[[Should caregivers prefer, in-person assessments will also be offered.**

Mental Health referrals to Stanford Outpatient Psychiatry Clinics will be offered to all participants who score 16+ on the CES-D at any assessment (see Section 2.A.3.e.6), in addition to participants who endorse symptoms of significant clinical concern, as determined by study staff. All participants are also provided information on accessing the VA Caregiver Support Program and the Veterans Crisis Line.]]

2.A.3.e.2. Education and Skill-Building Rehabilitation Intervention (ESBR)

Our ESBR intervention consists of four, 90-minute sessions over a 4-6 week period. **[[These four sessions are supplemented with booster sessions at 3 and 9 months post-intervention.]]** Each group session (\leq 10 participants) is attended either in-clinic or via video telehealth technology within the VAPAHCS.

As presented in the Summary of Section 2.A.1.D., the two modifiable risk factors for dementia care recipient placement in LTC are caregiver burden and depression.

Caregiver Burden

Our ESBR intervention consists of four, 90-minute sessions **[[plus booster sessions at 3 and 9 months post-intervention]]**. Each group (\leq 10 participants) session is attended either in-clinic or via video telehealth technology in place at community-based outpatient clinics, or other VA facilities, throughout VAPAHCS. ESBR is designed to decrease caregiver burden by altering caregiver perceptions of burden through education on dementia from several perspectives including: 1) simplified science that non-professionals care relate to and process; 2) reframing of cognitive, behavioral, and psychiatric symptoms of dementia as manifestations of damage to the brain of their loved one; and 3) understanding access to and being connected with VA, community, and national resources that can assist with reducing burden.

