The ESBR intervention is also designed to enhance caregiver self-efficacy and ability to seek appropriate additional education and resources on their own (e.g., through respected national organizations, responsible and reliable internet information). ESBR specifically provides communication skill-building designed to enhance caregiver and care recipient interactions with health care providers. Communication skill training targeting

caregiver ability to seek assistance from family, friends, VA, other providers, and community resources is also a key tenet of the ESBR intervention. ESBR encourages and provides support for caregivers to seek social work referrals VA (e.g., VA Caregiver Support Program, PACT clinic, GRECC clinic) to ensure caregivers, and their care recipients, are supported with all services for which they are eligible (e.g., support groups, respite care, home telehealth, home-based primary care, adult day health care).

Assistance and direction with planning for future care needs (e.g., LTC options, end-of-life care) is integrated into the intervention with the goal of anticipating future needs and reducing future burden.

Self-care and stress awareness/management are large foci of the ESBR intervention and are interwoven into each session. Participants will learn relaxation techniques including guided imagery, deep breathing, and progressive muscle relaxation. Sleep hygiene practices are discussed and solutions that incorporate fragmented caregiving schedules are problem-solved. Rationale for planning pleasant activities is discussed and pleasant event implementation is fostered.

Skill-building exercises specifically tailored to each group and reported caregiving challenges are integrated throughout the intervention (e.g., care recipient wandering, perseveration, agitation).

Caregiver Depression

The ESBR intervention is designed to address symptoms of caregiver depression through multiple modalities including: 1) behavioral activation and pleasurable event scheduling; 2) sleep hygiene skill-building; 3) stress management skill provision and relaxation training; and 4) respite care opportunities.

[[Relaxation Training

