Participants randomized to the Usual Care (UC) group will receive supplemental educational materials (e.g., VA Caregiver Support Program, Veterans Crisis Line, National Institute on Aging publications "Caring for a Person with Alzheimer's Disease: Your Easy-to-Use Guide" and "Understanding Memory Loss").

2.A.3.e.5. Follow-up (at 6, 12, and 24 months post-intervention)

Trained study staff, blind to the participants' ESBR/UC assignment, will administer follow-up assessments at 6, 12, and 24 months after the conclusion of the intervention or assignment to usual care. These assessments will mainly occur over the telephone. Our motivation for telephone assessment is to reduce study participation burden for the participants. Packets with assessment aids will be sent to the caregiver in the mail prior to each assessment. **[[Should caregivers prefer, in-person assessments will also be offered.]]** The follow-up assessments include clinicodemographic updates and measures of caregiver cognitive status, burden, depression, self-efficacy, and health-related quality of life, in addition to care recipient functional, placement, and mortality status. (See section 2.A.3.e.6. for a detailed description of these measures).

[[2.A.3.e.6. Study Conclusion

At the conclusion of the study, all participants will be thanked for their participation. Similar to referral procedures implemented throughout the study, at the conclusion of the study all participants will be provided with referrals for services for significant stress, mental health challenges, or cognitive concerns. Mental Health referrals to Stanford Outpatient Psychiatry Clinics will be offered to all participants. Participants with cognitive concerns will be offered referrals to the Stanford/VA Alzheimer's Research Center. The Center provides a comprehensive diagnostic evaluation, including cognitive assessment, by a multidisciplinary clinical research team at no cost.]]

2.A.3.e.6. Study Measures

Study assessments will mainly occur over the telephone τ , conducted by the Study Coordinator. Our motivation for telephone assessment is to reduce study participation burden for the participants. Packets with assessment aids will be sent to the caregiver in the mail prior to each assessment. **[[Should caregivers prefer, face-to-face (in-person) τ assessments will also be offered.]]**

Primary Outcome: Caregiver Burden

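### The models for community tenure, placement and survival (Hypotheses 3a-3c) leave out dementia subtype, the factor that randomization balances, and do not confine exploratory burden and depression covariates to baseline.

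*Combined protocol and SAP*

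**What the plan says.** Section 2.A.3.e.1 (Enrollment, Randomization, and Baseline Measures) uses a modified Efron procedure "to assure the three groups are comparable at baseline in terms of dementia subtype". Subtype is the only balancing factor named.

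Section 2.A.3.e.8a gives Hypothesis 3a (days of community tenure, mixed model), 3b (time to permanent long-term care placement, Cox) and 3c (time to death, Cox) the same two covariate sentences. The first fixes the adjustment set: "The model will be adjusted for effects of care recipient gender, income, and disease stage (Global Deterioration Scale score"). The second lists further candidates, among them "dementia subtype, and caregiver burden and depression will also be explored". No time-point is given for the covariates that are measured repeatedly. There is no rule for keeping a candidate, and no statement of which model carries the test.

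Elsewhere in the analysis plan, subtype appears only as an example of an exploratory moderator (Hypothesis 5).

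On the intended mechanism, Section 2.A.3.e.2 states that "the two modifiable risk factors for dementia care recipient placement in LTC are caregiver burden and depression". It adds that "ESBR is designed to decrease caregiver burden by altering caregiver perceptions of burden" and that "The ESBR intervention is designed to address symptoms of caregiver depression through multiple modalities". Both measures are taken at baseline and again at 6, 12 and 24 months (Section 2.A.3.e.5 and the assessment timeline).

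**The concern.** A factor used to constrain allocation belongs in the analysis. Balancing makes the treatment estimate less variable across randomizations. A model that omits the factor does not credit that gain, so its standard errors and tests no longer match the design. Leaving the factor to be explored also means that its inclusion can be decided after results are seen. Section 2.A.3.e.8b says the secondary analyses will put more weight on effect size than on p-values, to inform later trials, so a shrunken hazard ratio matters as much as a conservative p-value.

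The second issue is timing. Burden and depression are the route by which the intervention is meant to affect placement, and both are measured after randomization. If follow-up values were used as covariates, the part of the effect that acts through them would be removed. The text neither proposes this nor rules it out.

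**Working it through.** The documents give no power, event count or effect size for Hypotheses 3a-3c, so there is no stated figure to reproduce. The 0.83 power in Section 2.A.3.e.8b concerns Hypothesis 1 and does not bear on this point. The inputs taken from the plan are 150 caregivers analysed as 100 versus 50, a burden effect of 0.3 SD, and the covariate lists above. All other inputs are assumptions.

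**Hypothesis 3a (continuous outcome).** Let R² be the share of outcome variance explained by subtype. With good balance, omitting it inflates the reported standard error by 1/√(1 − R²):
- R² = 0.05: 1/√0.95 = 1.026
- R² = 0.10: 1/√0.90 = 1.054

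That is about 2.5-5% too wide. In sample-size terms it is like reporting the precision of 150 × 0.95 ≈ 142 or 150 × 0.90 = 135 participants instead of 150.

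**Hypotheses 3b and 3c (Cox).** That formula does not carry over. With a balanced three-level subtype (hazard ratios 1, 1.65 and 2.7, assumed) and about 19, 39 and 79 events, the ratio of unadjusted to adjusted standard error of the log hazard ratio was 0.9996, 0.999 and 0.998, so it is practically unchanged. The loss comes from elsewhere: the estimate is pulled towards 1, and under balance it varies less than its reported standard error implies. A simulation with N = 150, the same subtype hazard ratios and 69-85 events gave:

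| | Subtype omitted | Subtype included |
|---|---|---|
| Rejection when there is no effect | 3.8% | 5.5% |
| Power at hazard ratio 0.6 | 48% | 55% |

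These event counts are 46-57% of 150 (69/150 and 85/150). Fewer events would leave less to gain.

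**Burden and depression as covariates (conditional on which values are used).** If the intervention lowers burden by 0.3 SD and each SD of burden multiplies the placement hazard by H, the effect through burden is exp(−0.3 × ln H):
- H = 1.3: 0.92
- H = 2.0: 0.81

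A Cox simulation assumed H = 2.0, about 30% event risk over 24 months, and a correlation of 0.7 between baseline and follow-up burden. The treatment hazard ratios were:

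| | No burden covariate | Baseline burden | Follow-up burden |
|---|---|---|---|
| Effect wholly through burden | 0.85 | 0.84 | 1.02 |
| Equal direct effect added | 0.69 | 0.68 | 0.81 |

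Baseline adjustment did not attenuate the effect in any scenario run. Follow-up adjustment removed the mediated part only.

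**The case against.** A reader might infer that the plan as written adjusts the intervention effect away. The documents do not support this. Each hypothesis states one adjusted model, and burden and depression are not in it. They appear only in a list to be explored, next to age, gender and subtype, which are baseline characteristics. The Cox models run from randomization and mention no time-dependent covariates. Baseline values are the ordinary reading, and they are harmless. This objection stands, and it reduces the mediator issue to a missing restriction on timing.

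Two further inferences also fail. Disease stage is measured repeatedly, but no section says that the intervention changes it, so it should not be treated as lying on the causal path. The stated route through burden and depression leads to placement. Section 2.A.1.D adds hospitalization for burden, which bears on tenure. No route to survival is stated. Some components, such as respite and future-care planning, could also affect placement directly, so full mediation is not established.

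On subtype, it is fair to say that leaving it out cannot remove an effect, that these are secondary outcomes without a power claim, and that adding it has a price. Session 1 (Section 2.A.3.e.2a) names six common causes of dementia. Coded that way, subtype takes five parameters. With arm, gender, income and disease stage at one each, the model has nine. At an assumed 15-45 events this is 15/9 ≈ 1.7 to 45/9 = 5 events per parameter. That argues for collapsing sparse categories or stratifying, not for leaving the balancing factor optional.

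**Conclusion.** The concern holds in a limited form. The analyses of tenure, placement and survival do not include the factor on which randomization is balanced. The cost is moderate: a standard error about 2.5-5% too wide in 3a if subtype explains 5-10% of variance, and slightly conservative Cox tests with attenuated hazard ratios in 3b and 3c. The Cox figures (3.8% against 5.5%, 48% against 55%) come from one assumed scenario with many events and show direction and rough size only. If subtype is weakly prognostic, the loss is close to nil. Nothing here produces a false-positive result.

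The timing of burden and depression covariates is a secondary and conditional matter. It would distort the placement and tenure estimates only if follow-up values entered the model, which the plan does not propose.

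**What to change.** In Hypotheses 3a-3c, state one model for each outcome and name it as the model that carries the test: arm, dementia subtype in the categories used for randomization, care recipient gender, income and baseline disease stage. In 3b and 3c, subtype may enter as strata instead, and sparse categories should be collapsed by a rule fixed before unblinding. Keep the remaining candidates as labelled sensitivity analyses.

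Add one sentence that burden or depression, where explored as a covariate, enters as its baseline value only, and that follow-up values are used only in a separately labelled mediation analysis.

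The cost is SAP wording. Subtype is known at randomization, and the baseline measures are already scheduled. The one real downside is a few more parameters, or strata, when events are few. Hypotheses 1 and 2 name no covariates at all, so the sponsor may wish to settle the handling of subtype there at the same time.
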